## HYPOTHESIS

The hypothesis of this study is that BDQ-containing regimen is superior to rifamycin-containing regimen and increases the proportion of participants with sputum culture conversion in MGIT at Week 24 as compared to rifamycin-containing regimen.

## 4. STUDY DESIGN

### 4.1. Overall Design

This is a multicenter, randomized, open-label, active-controlled study to evaluate efficacy and safety of BDQ compared with rifamycin administered as part of a treatment regimen with CAM and EB for 48 weeks in adult participants with treatment-refractory MAC-LD.

- A target of 124 participants with treatment-refractory MAC-LD will be enrolled in this study. Participants who meet all the eligibility criteria will be randomized in a 1:1 (Treatment Group A [Group A]: Treatment Group B [Group B]) ratio:
  - Group A: BDQ + CAM + EB
  - Group B: rifamycin (RFP or RBT) + CAM + EB

For dosing details, refer to Section 6, [STUDY INTERVENTION AND CONCOMITANT THERAPY](#).

Participants will be randomly assigned to 1 of 2 treatment groups based on a computer-generated randomization schedule prepared before the study by or under the supervision of the sponsor. The randomization will be balanced by using randomly permuted blocks and will be stratified by country. The investigator and participant will be blinded for microbiological assessments until each participant has completed the other assessments at Week 24. If during the treatment period, the participant presents with clinical worsening, unblinding for microbiology assessments is allowed at the discretion of the investigator. For the microbiological blinding procedures, refer Section 6.3.

Participants who are taking rifamycin before start of the study intervention will be required to discontinue rifamycin to allow for a minimum of 14-day washout period. This safety measure is implemented to avoid DDIs between rifamycin and BDQ. Bedaquiline is a substrate of CYP3A4 (which is the main metabolic pathway for elimination) and co-administration with strong inducers such as rifamycin are contraindicated as they substantially reduce BDQ levels.

The study will consist of a screening period of 70 days (10 weeks) (including rifamycin washout period of 14 days for participants to whom this is applicable), an open-label treatment period of 48 weeks (baseline visit [Day 1] to Week 48) in Group A or 60 weeks (Day 1 to Week 60) in Group B, and a follow-up period of 12 weeks in Group A. Participants will return for study visits biweekly in the first 12 weeks and then every 4 weeks until Week 60. In addition, this study provides an option to receive BDQ-containing regimen for non-converters in Group B at Week 24 as the optional cohort. OPW-2 in optional cohort will be initiation of 2-week washout period in optional cohort.

Participants requiring a treatment regimen change will be considered treatment failures for subsequent endpoints and will be followed up for safety only, but all assessments should be performed according to the protocol. In addition to the option to switch to the optional cohort in Group B and withdrawal from the study, individualized treatment regimen was set up to as a regimen that may be used when participants are judged to have difficulty continuing their designated treatment regimen due to failure to respond (based on non-conversion supported by microbiological results, and clinical worsening of symptoms related to MAC-LD supported by the results such as chest computed tomography [CT] scan) or the occurrence of AE. Since the microbiological results are blinded, if the investigators consider the regimen change based on the clinical worsening of symptoms related to MAC-LD supported by the result of chest CT scan and so on, the investigators can consult with IDMC before the change. Specific switching criteria, treatment options, visits and assessments before and after switching, and follow-up will be detailed in Section 6.8.1, [Individualized Treatment Regimen](#).

Upon completion of the 48-week treatment period, the participants in Group A who achieved culture conversion will transfer to the follow-up period of 12 weeks. During the follow-up period, the converters will be treatment free for MAC-LD in order to confirm the durability of culture conversion. Non-converters at Week 48 in Group A will be discontinued from the study and switched to another treatment regimen if they continue chemotherapy because the duration of BDQ treatment is 48 weeks. On the other hand, the participants in Group B will continue the study intervention up to Week 60. Upon completion of the 60-week study intervention period, the study is completed, but the participant may continue SOC of local guidelines or medical practice at each study site for at least 1 year after culture conversion at the discretion of the investigators.

In addition, this study provides an option to receive BDQ-containing regimen (BDQ + CAM + EB) for non-converters in Group B at Week 24 as the optional cohort. The participants may continue Group B regimen, switch to an individualized treatment regimen, or BDQ-containing regimen in the optional cohort at the discretion of the investigators. The criteria for switching to optional cohort after Week 24 are detailed in Section 6.8.2. When the investigator changes to BDQ-containing regimen, 2-week washout of rifamycin is required before initiation of BDQ-containing regimen. The participants switching to BDQ-containing regimen will be considered treatment failures for rifamycin-containing regimen and will be followed up for efficacy and safety for BDQ-containing regimen.

In this optional cohort, during the 48-week treatment period (from Day 1 in optional cohort [OPD1] to Week 48 in optional cohort [OPW48]) of the study, participants may be changed to individualized treatment regimen. The investigators can postpone the decision to transfer to the optional cohort for up to Week 32 in order to confirm a sputum culture positive at Week 24, if necessary. Regardless of delay in the transition phase, the treatment duration of the optional cohort will be for 48 weeks.

All participants who switched to the optional cohort will be considered as treatment failure to rifamycin-containing regimen.

Key efficacy assessments include sputum culture conversion in MGIT and 7H10 or 7H11, St. George's Respiratory Questionnaire (SGRQ), and lung function (refer to Section 8.1, [Efficacy Assessments](#)). Key safety assessments will include the monitoring of AEs, physical examinations, measurement of body weight, vital sign measurements, clinical laboratory tests, 12-lead ECGs, and visual/audiology test (refer to Section 8.2, [Safety Assessments](#)).

An IDMC will be commissioned for this study. Refer to Committees Structure in Section 10.3, [Appendix 3: Regulatory, Ethical, and Study Oversight Considerations](#) for details.

A diagram of the study design is provided in Section 1.2, [Schema](#).

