## 1.2. Schema

Figure 1: Schematic Overview of the Study

Key: BDQ=bedaquiline; CAM=clarithromycin; CT=computed tomography; EB=ethambutol; IDMC=Independent Data Monitoring Committee; MAC=*Mycobacterium avium* complex; MAC-LD=MAC lung disease; max=maximum; OPW=week in optional cohort; RBT=rifabutin; RFP= rifampicin; W=Week; W/O=washout

Note:

- 1) OPW-2 - Initiation of 2-week washout period in optional cohort
- 2) OPD1 - Date of starting dose in optional cohort
- 3) OPW24 - Week 24 in optional cohort
- 4) OPW48 - Week 48 in optional cohort

- a Prior to Week 24, participants who are judged to have difficulty continuing their designated treatment regimen due to failure to respond (based on non-conversion and clinical worsening) or the occurrence of AE will be considered treatment failures and can switch to an individualized treatment regimen (see Section 6.8.1), at the discretion of the investigator in consultation with IDMC.
- b After Week 24 assessment, all participants who are judged to have difficulty continuing their designated treatment regimen due to failure to respond (based on non-conversion and clinical worsening) or the occurrence of AE will be considered treatment failures and will be given the option to switch to an individualized treatment regimen (see Section 6.8.1) at the discretion of the investigator.
- c After completion of 48-week treatment, converters who achieved culture conversion at Week 48 in the Group A will be followed for 12 weeks as drug-free period. Participants who failed to achieve sputum culture conversion (non-converters) by Week 48 and continue chemotherapy will be discontinued from the study and switched to another treatment regimen.
- d At Week 24, non-converters in the Group B, will be considered to switch to BDQ-containing regimen at the discretion of the investigators. When the investigator changes to BDQ-containing regimen, 2-week washout of used rifamycin is required before initiation of BDQ-containing regimen.
- e All participants who are judged to have difficulty continuing their BDQ-containing regimen due to failure to respond (based on non-conversion and clinical worsening) or the occurrence of AE will be considered treatment failures and will be given the option to switch to an individualized treatment regimen (see Section 6.8.1) at the discretion of the investigators.

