## Clinical Studies

### *Phase 1 Studies*

Pooled analyses were done for 8 Phase 1 studies in healthy subjects (5 single-dose studies and 3 multiple-dose studies). The pooled analysis included data from 217 healthy subjects, of whom, 189 received at least 1 dose of BDQ up to 700 mg. Five studies were not included in the Phase 1 pooled analysis: C117 was an open-label, DDI study in 16 HIV-1 infected subjects (without TB infection). This single-sequence DDI Phase 1 study was conducted to investigate the potential interaction between steady-state nevirapine and a single-dose of 400 mg BDQ. C112 was an open-label, single-dose study in 8 healthy subjects and in 8 subjects with moderate hepatic impairment. TBC1003 was a double-blind, single-dose study in 88 healthy subjects to evaluate the effect of a single supratherapeutic (800 mg) dose BDQ on the QT/corrected QT (QTc) interval. A total of 44 subjects received BDQ. TBC1002 was an open-label 3-way crossover study in 36 healthy adults to assess the relative bioavailability of 2 pediatric formulations of BDQ after single-dose administration of 100 mg, with and without food. NTM1001 was an open-label, DDI study in 16 healthy subjects. This single-sequence DDI Phase 1 study was conducted to investigate the potential interaction between steady-state CAM and a single-dose of 100 mg BDQ.

Bedaquiline was well absorbed with  $t_{\max}$  at approximately 5 hours postdose. The  $C_{\max}$  and AUC increased proportionally up to the highest doses studied (700 mg single dose and 400 mg once daily [qd] multiple doses). Accumulation from Day 1 to Day 14 was approximately 2-fold expressed as increase in AUC, corresponding to an effective half-life of about 24 hours. From Phase 2 study, 4 weeks after ceasing BDQ intake, the mean BDQ and M2 concentrations were reduced by approximately 40% compared to the end of the BDQ treatment period. At the last follow-up visit (Week 120), BDQ and M2 plasma concentrations were approximately 15% and 20% of the median Week 24 plasma concentrations, respectively. The average  $t_{1/2 \text{ term}}$  of BDQ and M2, was estimated as 5.5 months and 5.3 months, respectively.

Administration of BDQ as the tablet formulation with food increased the relative bioavailability (by 95%) compared to administration without food.

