The standard duration of administration with BDQ for the treatment of MDR-TB with a known bactericidal effect is 24 weeks, whereas the duration of administration with BDQ for MAC-LD, where a bacteriostatic effect is suggested, needs to be longer, and is therefore set at 48 weeks and drug free follow-up period for 3 months is planned to evaluate the recurrences after completion of treatment to evaluate appropriate treatment duration. On the other hand, the participants in Group B who achieved culture conversion at Week 24 will continue up to Week 60. This 60-week duration is consistent with the end of follow-up period in Group A. Upon completion of the 60-week study intervention period, the study is completed, but the participant may continue SOC of local guidelines in Japan, South Korea and Taiwan or medical practice at each study site for least 1 year after culture conversion at the discretion of the investigators after study completion.

In addition, participants who have not achieved culture conversion in Group A (BDQ-containing regimen) will continue their assigned regimen until Week 48, unless they have difficulty continuing due to failure to respond (see Section 6.8.1, based on non-conversion and clinical worsening) or the occurrence of AE related to the regimen. If participants were judged to have difficulty continuing due to failure to respond to the regimen or the occurrence of the regimen related AE, at the discretion of investigators, there will be options to discontinue from the study or switch to an individualized treatment regimen (in principle, add on injectable SM, injectable or inhalation suspension of AMK).

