    - Practicing a highly effective method of contraception (failure rate of <1% per year when used consistently and correctly) and agrees to remain on a highly effective method while receiving study intervention and until 90 days after last dose - the end of relevant systemic exposure. The investigator should evaluate the potential for contraceptive method failure (eg, noncompliance, recently initiated) in relationship to the first dose of the study intervention. Examples of highly effective methods of contraception are located in Section 10.5, [Appendix 5: Contraceptive Guidance](#).

12. a woman must agree not to donate eggs (ova, oocytes) or freeze for future use for the purposes of assisted reproduction during the study and for at least 90 days after receiving the last dose of study intervention.
13. a male participant must wear a condom when engaging in any activity that allows for passage of ejaculate to another person during the study and for at least 90 days after receiving the last dose of study intervention (male participants should also be advised of the benefit for a female partner to use a highly effective method of contraception as condom may break or leak).
14. a male participant must agree not to donate sperm for the purpose of reproduction during the study and for a minimum 90 days after receiving the last dose of study intervention.

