- neuroleptics: phenothiazines thioridazine, haloperidol, chlorpromazine, trifluoperazine, pericycline, prochlorperazine, fluphenazine, sertindole, and pimozide
- quinolone antimalarials (eg, chloroquine and quinacrine)
- moxifloxacin (prohibited from the initiation date of BDQ treatment up to 1 month after the last dose of BDQ)
- antimicrobials: erythromycin intravenous (IV), pentamidine, delamanid
- tricyclic antidepressants, including amitriptyline, doxepin, desipramine, imipramine, and clomipramine
- prokinetic cisapride
- nonsedating antihistamines: astemizole, terfenadine, and mizolastine
- clofazimine (increased QT prolongation is reported in co-administration with BDQ)

**NOTE:** The above list of drugs with known risk of QT prolongation is based on drugs that may be commonly used during the treatment of NTM-LD. The investigator should consult current publicly available drug information to identify other drugs with potential QT prolongation. The list of potential QT prolonging drugs is long and subject to change. Clinical interpretation of known and potential additive risks is required.

The following medications are prohibited because of their potential for muscle damage (myopathy) from 7 days prior to Day 1 up to the last dose of study interventions and combination drugs (CAM and EB) (including individualized treatment regimens) (see note):

- 3-hydroxy-3-methylglutaryl-coenzyme A reductase inhibitors (statins)
- griseofulvin

**NOTE:** All prohibited medications with a risk for muscle damage (myopathy) can be (re-)started 1 month after BDQ discontinuation.

Hepatotoxic medications should be used with caution, especially during the treatment period in participants with signs of hepatotoxicity (eg, participants with transaminase elevations). Alternative medications should be used if possible.

For participants who change their treatment regimen, latest package inserts should be consulted for contraindicated medication(s) or medication(s) that is not recommended for concomitant use.

The sponsor must be notified in advance (or as soon as possible thereafter) of any instances in which prohibited therapies are administered.

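### The 12-week Group A follow-up is called drug-free and used to judge durability and treatment duration, yet the protocol's own pharmacokinetic figures imply about half of the end-of-treatment bedaquiline concentration remains at Week 60

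*Protocol*

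**What the plan says.** Protocol 4.1 plans "a follow-up period of 12 weeks in Group A". Footnote c of the schema (1.2) says that Week 48 converters "will be followed for 12 weeks as drug-free period". Section 4.1 states the purpose: "During the follow-up period, the converters will be treatment free for MAC-LD in order to confirm the durability of culture conversion". Section 4.2 adds that a "drug free follow-up period for 3 months is planned to evaluate the recurrences after completion of treatment to evaluate appropriate treatment duration".

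Two Week 60 results draw on this period. Protocol 9.4.4 and SAP 5.4.2.2.2 compare Week 60 conversion between the groups by a stratified Cochran-Mantel-Haenszel test. SAP 5.5.2 counts culture reversion up to Week 60 and no further.

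On persistence, Protocol 2.2 (Phase 1 Studies) reports from a Phase 2 study that 4 weeks after stopping, "the mean BDQ and M2 concentrations were reduced by approximately 40% compared to the end of the BDQ treatment period". It also gives BDQ and M2 at about 15% and 20% of the median Week 24 concentration at Week 120, and average terminal half-lives of 5.5 and 5.3 months.

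BDQ sampling ends at Week 48 (Protocol 1.3 and 8.4.1), and SAP 5.7.1.2 derives no exposure later than that. Section 8.2.3 cites the drug's long half-life when it sets ECG follow-up. The text that justifies the 12-week period does not mention it.

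**The concern.** Twelve weeks is about half of one terminal half-life. What Group A undergoes after Week 48 is therefore a slow taper of BDQ and M2 after clarithromycin and ethambutol have stopped, not a period without drug.

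The protocol's own reasoning makes this relevant. Section 2.1 suggests that BDQ is at least bacteriostatic against MAC. Section 4.2 sets 48 weeks because a bacteriostatic effect is suggested. The mouse work in 2.2 found BDQ monotherapy still bacteriostatic after four months. With such an agent, a negative culture may reflect suppression rather than clearance.

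A low reversion rate at Week 60 could then be read as drug-free durability and as support for a 48-week course. Recurrence that appears only after BDQ has largely cleared would fall outside observation.

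**Working it through.** The documents state no residual concentration at 12 weeks, so there is no plan figure to reproduce. The estimate is built from the figures in Protocol 2.2.

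**Inputs**
- Remaining at 4 weeks: 1 - 0.40 = 0.60 (BDQ and M2).
- Terminal half-life, at 4.348 weeks per month: BDQ 5.5 months = 23.9 weeks; M2 5.3 months = 23.0 weeks.
- Remaining at Week 120: 0.15 (BDQ), 0.20 (M2). If dosing ended at Week 24 (an assumption), this is 120 - 24 = 96 weeks after stopping.
- Follow-up: 12 weeks.

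**Fraction of the end-of-treatment plasma concentration left at 12 weeks**

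| Method | BDQ | M2 |
|---|---|---|
| 60% at 4 weeks, then terminal half-life: 0.60 × 2^(-8/half-life) | 0.476 | 0.472 |
| Log-linear from 60% at 4 weeks to 15% (20%) at 96 weeks | 0.532 | 0.545 |
| Half-life alone: 2^(-12/half-life) | 0.706 | 0.697 |

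For the second row the implied BDQ half-life is 92 × ln 2 / ln(0.60/0.15) = 46 weeks, and 0.60 × 2^(-8/46) = 0.532. For M2 the implied half-life is 58.0 weeks.

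**Sensitivity.** Moving the 4-week residual to 55% or 65% in the first row gives 44% or 52% for BDQ.

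**Profile.** By the first method BDQ is at about 60%, 53% and 48% at Weeks 52, 56 and 60. It reaches 10% only at 4 + 23.9 × log2(0.60/0.10), about 66 weeks after the last dose.

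**Readings that would give less**
- Continuing a 40% fall every 4 weeks gives 0.60^3 = 0.22 at 12 weeks. By 96 weeks it gives 0.60^24, effectively zero, against the stated 15%.
- The effective half-life of about 24 hours in 2.2 describes accumulation from Day 1 to Day 14. Applied to washout, it leaves essentially nothing at 4 weeks, against the stated 60%.

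**Consistency of the inputs.** The figures do not fit one exponential. A 5.5-month half-life alone predicts 89% at 4 weeks (stated 60%) and 6% at 96 weeks (stated 15%). Decline in several phases, and a mix of means, medians and an average half-life, can explain this, so it is not treated as an error.

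**The case against.** The strongest reply is that the documents give no numerical MIC of BDQ for MAC, only that it is low, and that the firm bacteriostatic finding comes from mice. A reader might infer that residual BDQ does suppress cultures at Week 60. That is not supported; only the possibility is.

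Second, the wording in 4.1 is literally true, because no MAC-LD treatment is given. Section 4.2 states an aim and draws no conclusion that 48 weeks is adequate. Both points stand. The difficulty lies in the drug-free label in 1.2 and 4.2, and in an aim the period cannot meet by itself.

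Third, Group B is still on its full regimen at Week 60, so residual BDQ does not simply favour Group A. This stands too. The limit concerns what the Group A result says about durability, not a bias of known direction between groups.

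Fourth, the decline figures come from another study. This trial doses for 48 weeks with clarithromycin, which the model in 4.3 credits with a 37% reduction in BDQ clearance and which stops together with BDQ. Table 1 puts simulated Week 48 exposure at 0.95 to 0.99 of the MDR-TB regimen. Similar residual fractions are plausible but unmeasured.

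A reader might also infer that the pharmacokinetic figures contradict the safety windows. They do not. Criterion 11 in 5.1 says "while receiving study intervention and until 90 days after last dose - the end of relevant systemic exposure", and no threshold for relevance is given that a percentage could breach. Routine ECGs continue through Week 60 (1.3). The 4-weeks-after-last-dose rule in 8.2.3 concerns weekly ECGs in participants whose QTcF prolongation has not resolved.

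**Conclusion.** The concern holds as one of description and inference. On the protocol's own figures, about 47 to 55% of the end-of-treatment plasma BDQ and M2 concentration would remain at Week 60, or about 70% from the half-life alone. This rests on dosing in the earlier study having ended at Week 24, and on a similar decline after 48 weeks of BDQ with clarithromycin stopping at the same time.

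The period is off-dosing but not drug-free. Group A's Week 60 conversion and reversion results cannot by themselves establish drug-free durability or the adequacy of 48 weeks.

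The Week 24 primary endpoint is unaffected. Week 60 conversion is a supportive secondary endpoint and reversion is exploratory, so the weight falls on the stated durability and duration aims.

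**What to change.** 1. In Protocol 1.2, 4.1 and 4.2, describe Weeks 48 to 60 in Group A as off-dosing with BDQ and M2 still present. State that the Week 60 conversion and reversion results show maintenance 12 weeks after the last dose under residual BDQ, and are not by themselves evidence of drug-free durability or of the adequacy of 48 weeks.
2. In SAP 5.7.1.2, use the planned population PK model to predict BDQ and M2 at Weeks 52, 56 and 60 for Group A participants in follow-up. Present the predictions beside Week 60 conversion and reversion. Label them as extrapolation, because no PK sample is taken after Week 48 and clarithromycin stops then.
3. At most, ask the sponsor to reconcile with 2.2 the 90-day wording in criterion 11 and the differing ends of the prohibited-drug lists in 6.8. One entry reads "moxifloxacin (prohibited from the initiation date of BDQ treatment up to 1 month after the last dose of BDQ", while the rest of the QT list ends at the last dose. No duration is proposed here.

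No extra blood sample is requested. The Table 4 maxima already sum to the stated ceiling (24 + 30 + 7.5 + 2 + 52 = 115.5 mL), so a further 2 mL would exceed it.

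The cost is revised wording and additional output from a model already planned. The price is a more modest durability statement.
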